Patients with stable angina with evidence for at least >10% perfusion defect (moderate to large ischemia) or patients with troponin-negative unstable angina.

Exclusion Criteria: A need for oral anticoagulation therapy; an increased risk of bradycardia, and concomitant therapy with a strong cytochrome P-450 inhibitors; surgery<4 weeks; The use of any thienopyridines prior to randomization; upstream use of GP IIb/IIIa inhibitors; bleeding diathesis or major bleeding episode within 2 weeks; thrombocytopenia; incessant chest pain; hemodynamic instability; NSTEMI as evidenced by elevation of troponin levels; renal failure with a serum creatinine >2.0 mg/dL; and anemia with HCT<30%.

Methods

In this study, 100 patients with stable angina or troponin negative unstable angina, will be randomized to ticagrelor loading dose versus clopidogrel loading dose and eptifibatide bolus only administrated before PCI. Platelet function testing will be performed at baseline, at 30 min post-loading dose, 2 h, and 4 h, and 24 h. All patients will be started on aspirin 81 mg prior to procedure . Heparin 60 units/kg will be administered intravenously before PCI. PCI will be performed in accordance with standard clinical practice. Please see Fig. 2, Design of the study below and Table 1.

Fig. 2

Blood Sampling for Platelet Function Testing

Blood will be collected from an antecubital vein into vacutainer tubes (Becton-Dickinson, Franklin Lakes, NJ) that contain 3.2% trisodium citrate for light-transmittance aggregometry. All measurements will be performed at the UAB thrombosis research laboratory.

Light-Transmittance Aggregometry

Platelet aggregation induced by ADP (5 and 20 μm), TRAP (10 and 20 μm) platelet-rich plasma will be measured with a Chronolog Optical Aggregometer (model 490-4D; Chronolog Corporation, Havertown, Pa). The final extent of aggregation, measured at 6 minutes after agonist addition, and the maximal extent of aggregation will be expressed as the percent change in light transmittance from baseline with platelet-poor plasma as a reference. Inhibition of platelet aggregation (IPA) will be calculated as follows:

$$\text{IPA}(\%) = 100\% \times \frac{\text{PA}_t - \text{PA}_b}{\text{PA}_b}$$

Where PA is platelet aggregation, b is predosing, and t is postdosing.

Statistical Analysis

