The present study is an exploratory trial to investigate the percent inhibition of platelet activity (%IPA) (measured by light-transmittance aggregometry) comparing the loading dose of ticagrelor

with loading dose of clopidogrel and 2 boluses of eptifibatide measured at all time-points. Since there are no preliminary data available, no power calculation was performed. Statistical analysis will be performed using the Statistical Package for Social Sciences, version 22.0, software package for Windows (SPSS, Inc., Chicago, Illinois). Data will be presented as mean \pm 1 SD or frequencies; a value of $P < 0.05$ will be considered statistically significant. %IPA of ticagrelor and 2 boluses of eptifibatide vs. loading dose of clopidogrel and 2 boluses of eptifibatide will be compared at all time-points using repeated measures ANOVA. Continuous variables will be compared between the 2 treatment groups with Student t test. For comparisons of categorical data, the Chi-Square test will be performed.

End-Points

The primary end point of the study is to compare %IPA induced by ADP at 2 h, in patients randomized to the loading dose of ticagrelor with loading dose of clopidogrel and 2 boluses of eptifibatide measured at 2 h post loading dose. Secondary endpoints of the study are to compare %IPA induced by ADP and TRAP in patients randomized to the loading dose of ticagrelor with loading dose of clopidogrel and 2 boluses of eptifibatide at all time-points. Other secondary outcomes include: 1) the occurrence of post-procedural myonecrosis comparing the 2 groups. Ischemic myonecrosis will be defined as elevated post-procedure troponin-1 level $>0.26 \mu\text{g/l}$; and 2) the rate minor (a fall in hemoglobin of 3 to $<5 \text{ g/dL}$) and major bleeding (a fall in the hemoglobin $>5 \text{ g/dL}$) between the groups.

Anticipated Findings

Since platelet inhibition with ticagrelor starts rapidly, we expect that %IPA at 2 h will be no significantly different than clopidogrel and eptifibatide bolus. In addition, since eptifibatide half-life is short, we expect that %IPA at 24 h will be higher with ticagrelor than clopidogrel and eptifibatide bolus.

We anticipate the results of the present study will set the stage for a large randomized trial comparing myonecrosis, stent thrombosis, death, myocardial infarction, bleeding, and costs in patients randomized to ticagrelor only vs. loading dose of clopidogrel and 2 boluses of eptifibatide.

Table 1: Schedule of treatment

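### The %IPA comparisons use no baseline covariate although baseline aggregation is measured in every patient: a low-cost improvement of uncertain size, not an error

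*Combined protocol and SAP*

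**What the plan says.** The Statistical Analysis section gives two methods for continuous outcomes. For %IPA over time, the last part of the sentence reads "loading dose of clopidogrel and 2 boluses of eptifibatide will be compared at all time-points using repeated measures ANOVA". More generally, "Continuous variables will be compared between the 2 treatment groups with Student t test". Neither sentence mentions a covariate, and no other section does. (The first part of the ANOVA sentence describes the ticagrelor arm differently from Methods and End-Points. Those passages must be reconciled, but the present point does not depend on it.)

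End-Points sets the primary comparison: "The primary end point of the study is to compare %IPA induced by ADP at 2 h". ADP and TRAP at all time-points are secondary.

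Baseline is collected. Methods states "Platelet function testing will be performed at baseline, at 30 min post-loading dose, 2 h, and 4 h, and 24 h", and Table 1 marks platelet function testing at baseline. Under Light-Transmittance Aggregometry, %IPA is the percent change from the predosing value ("Where PA is platelet aggregation, b is predosing, and t is postdosing"). That section also lists ADP at 5 and 20 µM and two readouts: "The final extent of aggregation, measured at 6 minutes after agonist addition, and the maximal extent of aggregation".

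The plan makes no power claim: "Since there are no preliminary data available, no power calculation was performed".

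**The concern.** Dividing by baseline is not the same as adjusting for it. A percent change is free of baseline only if postdose aggregation is, on average, proportional to baseline. The documents neither state nor test this. If it fails, %IPA still varies with baseline within each arm. That variation then adds noise to the arm difference, and a chance baseline imbalance shifts the estimate. A covariate would remove both effects, using a value already in the data set.

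What is at stake is precision and robustness in an exploratory trial of 100 patients. Validity is not at stake, and no stated power is undermined.

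**Working it through.** The plan gives no SD, target difference or power for %IPA, so there is no figure of its own to reproduce.

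**Inputs from the documents.** Total of 100 patients (Methods). From the earlier 70-patient study described in the background, reading ± as SD: TRAP at 6 h, 87 ± 13 vs 74 ± 17; ADP 5 µM at 2 h, 100 ± 0.01 vs 99 ± 0.25, and at 6 h, 99 ± 2.4 vs 99 ± 1.2.

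**Assumed, not in the documents.** 50 per arm; baseline aggregation mean 75, SD 12 (8 to 16 as sensitivity); baseline-postdose correlation 0 to 0.6; aggregation floored at zero.

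**Step 1: what percent change leaves behind.** Sign %IPA so that inhibition is positive (variance ratios do not depend on the sign): 100 × (1 − PA_t/PA_b). If PA_t averages a + k × PA_b, this becomes 100 × (1 − k − a/PA_b). Baseline drops out only when a = 0. Baseline cannot help as an extra ANOVA time-point either, because there PA_t = PA_b and %IPA is 0 for everyone.

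**Step 2: the size in principle.** Let r be the within-arm correlation of baseline with %IPA (not with postdose aggregation). With 98 degrees of freedom before adjustment and a normally distributed baseline, adjusted over unadjusted variance is about (1 − r²) × (1 + 1/(98 − 2)).
- r = 0: 1.01.
- r = −0.24: 0.942 × 1.010 = 0.95.
- r = 0.34: 0.884 × 1.010 = 0.89.

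A simulation with baseline 70 ± 12 (4,000 trials per scenario) agrees: 1.01 with proportional response, 1.00 near the ceiling, 0.95 at r about −0.24 and 0.89 at r about 0.34.

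**Step 3: calibrated scenarios.** Simulation, 20,000 trials each, baseline SD 12. Entries are variance ratios by baseline-postdose correlation.

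| Scenario | 0 | 0.15 | 0.3 | 0.45 | 0.6 |
|---|---|---|---|---|---|
| TRAP 6 h values | 0.952 | 1.001 | 1.002 | 0.943 | 0.815 |
| ADP 6 h values | 1.001 | 1.012 | 0.988 | 0.936 | 0.851 |
| Repeated measures, 2 h, own slope per time-point | 0.985 | 1.011 | 0.989 | 0.918 | 0.798 |
| Repeated measures, 2 h, one shared slope | 1.083 | 1.085 | 1.032 | 0.939 | 0.802 |

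Other scenarios with similar arms (postdose mean 5 to 45) gave 0.90 to 1.01 at correlations 0.15 to 0.45, and 0.80 to 0.99 at the two ends. Dissimilar arms gave 0.95 to 1.01 in the middle. The middle is flat because the dependence vanishes where the slope on baseline equals the ratio of mean postdose to mean baseline aggregation. For the TRAP values, ignoring the floor and taking the postdose SD as 0.75 times the %IPA SD, that happens at correlations near 0.26 × 12/12.75 = 0.24 and 0.13 × 12/9.75 = 0.16.

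**Step 4: in percentage points.**
- TRAP values: unadjusted 95% half-width 1.984 × √((13² + 17²)/50) = 6.0. At correlation 0.45 it is 6.0 × √0.943 = 5.8, or 3% narrower.
- Largest gain with SD 12: √0.80 = 0.89, or 11% narrower.
- ADP 2 h values: 1.984 × √((0.01² + 0.25²)/50) = 0.07. Even 20% less variance saves 0.07 × (1 − 0.89), which is under 0.01 point.

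**Step 5: chance imbalance.** One standard error of the baseline difference is 12 × √(2/50) = 2.4 points. With the TRAP values this moves the unadjusted difference by 0.2, 0.3 and 0.8 points at correlations 0.15, 0.3 and 0.45. Across scenarios at SD 12, the unadjusted difference correlated with baseline imbalance by up to 0.46; after adjustment the correlation was within 0.02 of zero.

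**Step 6: validity and cost.** Unadjusted interval coverage was 94.5% to 95.4%, falling to about 93% near the ceiling with or without adjustment. At 67:33 allocation with dissimilar arms and a common slope, one set of simulations gave ratios up to about 1.03 and another up to 1.08.

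**The case against.** The strongest reply is that nothing is wrong. The comparison is valid, each outcome is already scaled to the patient's own baseline, and the documents say nothing about the dependence left after that scaling. The only documented ADP figures at 2 h, the primary agonist and time, imply a gain under 0.01 point. The TRAP calibration uses a secondary agonist at 6 h, which is not a sampling time here, in arms unlike this trial's. The remedy also has conditions: the 1% cost assumes 1:1 allocation, which is not stated, and the covariate is undefined while two ADP concentrations and two readouts leave 2 × 2 = 4 candidate primary variables.

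Much of this stands. The gain is unknown and may be nil for the primary end point, and both conditions must go into the fix. Two parts do not defeat the point. Scaling by baseline removes the dependence only under proportionality (step 1). And the near-complete 2 h ADP inhibition came from arms that both received ticagrelor with eptifibatide; the documents give no %IPA for ticagrelor alone, so a ceiling cannot be taken for granted.

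A reader might infer that the planned analysis is biased, or that the trial gives up a material amount of power. The documents support neither: randomisation protects the unadjusted comparison, no power is claimed, and the correlation needed to show a material gain is not given.

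**Conclusion.** The point holds as an optional, low-cost improvement. No baseline covariate is planned although one is available for every analysable patient. Under the assumptions above (50 per arm, baseline 75 ± 12, correlation 0 to 0.6), the variance ratio is about 0.8 to 1.01. In the middle of the range the gain is nil to small. The larger gains occur only towards the ends of the assumed range, and near-complete 2 h ADP inhibition would make the benefit negligible in absolute terms. The steadier benefit is that the estimate no longer moves with chance baseline imbalance. Adjustment would not repair the slight undercoverage near the ceiling. The case rests on the low cost and on settling the choice before the data are seen; confidence in the size is limited because its main determinant is unknown.

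**What to change.** In Statistical Analysis and End-Points:

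1. Name the single primary variable: one ADP concentration, and final or maximal aggregation.
2. Prespecify a linear model for 2 h %IPA with arm and the patient's baseline aggregation for that same agonist, concentration and readout. Report the adjusted difference with its 95% CI.
3. In the repeated measures analyses of ADP and TRAP, use the matching baseline with a baseline-by-time term. One slope shared over time raised the 2 h variance by up to 9% in the check above.
4. Keep %IPA as the outcome scale and the unadjusted means as descriptive. State that a slope common to both arms is an approximation.
5. State the allocation ratio. If it is unequal and slopes may differ by arm, centre baseline and add an arm-by-baseline term.

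The cost is document wording plus the choice in item 1, and one degree of freedom of 98 at 2 h (one per time-point in the repeated measures model). Variance is at worst about 1% larger under 1:1 allocation, and could be a few percent more with unequal allocation and different slopes if item 5 is not followed. No new data are needed, and no patient is lost, since %IPA already requires the baseline value.

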We recently randomized 70 patients with Non-ST-Segment Myocardial Infarction (NSTEMI) to ticagrelor 190 mg loading and eptifibatide bolus-only (TEP) vs. ticagrelor loading and eptifibatide bolus plus 2 h infusion (TEPI) administered before stenting [Fig. 1]. Light transmission aggregometry was performed and percent inhibition of platelet aggregation (%IPA) was calculated at baseline, and at 2, 6, and 24 h using ADP, TRAP, collagen, and arachidonic acid (AA). Cardiac enzymes, hemoglobin and hematocrit were measured at baseline and at 24 h. The event rates were determined at 30-day follow-up. We demonstrated that in patients randomized to TEP vs. TEPI, there were no significant difference in the %IPA values at 2 h and 6 h with ADP 5 μ M ($100\% \pm 0.01$ vs. $99\% \pm 0.25$ and $99\% \pm 2.4$ vs. $99\% \pm 1.2$, respectively) and with ADP 20 μ M as well as with collagen. However, %IPA was lower at 24 h (still >60% platelet inhibition) compared with that at 2 h and 6 h. Percent IPA with TRAP 10 or 20 μ M was higher at 6 h in patients randomized to

TEPI vs. TEP ($87\% \pm 13$ vs. $74\% \pm 17$; $P < 0.01$, respectively), but this had no bearing on outcomes since ADP was highly inhibited by ticagrelor at 6 h. There were no significant differences in troponin or hemoglobin levels among the groups. During follow-up, and there was no stent thrombosis or myocardial infarction.

We concluded that %IPA values with ADP and collagen were not significantly different comparing ticagrelor with eptifibatide bolus only vs. ticagrelor and eptifibatide bolus plus 2 h infusion. Eptifibatide bolus only highly inhibited platelets aggregation while allowing bridging to the antiplatelet effect of ticagrelor and circumventing the need for continuous eptifibatide infusion. There was no significant difference in bleeding or MI between the 2 groups.

RATIONALE

The antiplatelet effect of clopidogrel is slow in onset, variable, and irreversible; approximately 15 to 30% of patients are non-responsive [6]. Furthermore, a 75-mg/d clopidogrel maintenance dose requires at least 5 days, and a 600-mg loading dose of clopidogrel requires up to 8 hours to achieve a 50% steady state of inhibition of ADP-induced platelet aggregation [7-9]. The difference in the clinical effects of ticagrelor compared with clopidogrel lies in the fact that ticagrelor exerts more rapid, more potent, and more consistent inhibition of platelets [10,11]. In the CLEAR

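### The planned Student t test and repeated measures ANOVA make no allowance for %IPA spread that probably differs by arm and time; Welch and a sphericity-corrected test would, at no cost

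*Combined protocol and SAP*

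**What the plan says.** The End-Points section makes ADP-induced %IPA at 2 h primary, and %IPA with ADP and TRAP at all time-points secondary. Methods schedules samples at baseline, 30 min, 2 h, 4 h and 24 h in 100 patients.

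On analysis, the Statistical Analysis section says that %IPA in the two arms "will be compared at all time-points using repeated measures ANOVA", and then: "Continuous variables will be compared between the 2 treatment groups with Student t test". Significance is set by "a value of $P < 0.05$ will be considered statistically significant". For display, "Data will be presented as mean \pm 1 SD or frequencies".

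The section does not mention an unequal-variance t test, a sphericity correction, the error term for comparisons at single times, or which of the two methods serves the primary 2 h comparison.

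The only figures on the spread of %IPA are in the background account of the sponsor's earlier 70-patient study. For ADP 5 µM the ± values, eptifibatide bolus only vs bolus plus infusion, are 0.01 vs 0.25 at 2 h and 2.4 vs 1.2 at 6 h. The text does not label them as SD or SE.

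**The concern.** Student t assumes the same variance in both arms. The within-patient tests of repeated measures ANOVA also assume sphericity: differences between any two times have the same variance. Percent inhibition close to its 100% ceiling has little room to vary, and values further down can vary widely. The pilot values fit that pattern.

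This trial's design should strengthen it. As Methods and End-Points describe the arms, only the comparator receives eptifibatide. The Rationale calls clopidogrel's effect slow and variable, with 15 to 30% non-responders. Anticipated Findings expects ticagrelor to be ahead by 24 h because eptifibatide is short-lived. On the sponsor's own account, spread should differ between arms and change over time.

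Anticipated Findings also predicts no significant difference at 2 h. An error estimate that is too large at 2 h would favour that result whatever the data show. One that is too small at 24 h would favour the predicted ticagrelor advantage.

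**Working it through.** The plan gives no figure to reproduce: "Since there are no preliminary data available, no power calculation was performed". Alpha is taken as two-sided 0.05 and allocation as 50/50, since neither is stated. All simulations use normal data with no true difference.

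**1. The pilot values.** Ratios between arms are 0.25/0.01 = 25 at 2 h and 2.4/1.2 = 2 at 6 h. Within arm across times they are 2.4/0.01 = 240 and 1.2/0.25 = 4.8. If the values are SEs with 35 per arm (assumed), multiplying by √35 = 5.92 gives SDs of about 0.06, 1.5, 14 and 7. The ratios are unchanged, so spread is unequal on either reading.

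**2. Student t at one time.** Compare the pooled SE, sp·√(1/n1 + 1/n2), with the true SE, √(s1²/n1 + s2²/n2). With n1 = n2 they are identical. Assumed SDs are 15 (arm 1) and 1 (arm 2):

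- 50 vs 50: both SEs 2.126; rejection 5.3%.
- 45 vs 50: sp² = (44·225 + 49·1)/93 = 106.98; pooled SE 2.125, true SE 2.241, ratio 0.95; about 6.6%.
- 40 vs 50: sp² = (39·225 + 49·1)/88 = 100.27; pooled SE 2.124, true SE 2.376, ratio 0.89; about 8%.
- 50 vs 40: sp² = (49·225 + 39·1)/88 = 125.73; pooled SE 2.379, true SE 2.127, ratio 1.12; about 3%.

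Welch stays at about 5% in every case. With the pilot's 2 h values read as SDs, Student t gives 5.3% at 50/50, and 3.2% or 8.0% at 45/55, depending on which arm is larger.

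**3. Overall arm-by-time test.** The documents give no SDs for this trial's arms. Assumed SDs at 30 min, 2 h, 4 h and 24 h are 30, 15, 8, 15 (ticagrelor) and 5, 2, 5, 20 (comparator), with correlation 0.5 and 50 per arm. The uncorrected F test rejects about 7% (6.6 to 7.2% over repeated runs), and Greenhouse-Geisser about 5%. With only the pilot's two times, where sphericity cannot fail, the arm and arm-by-time tests keep about 5%.

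**4. Time-specific contrasts, if built on an error pooled over times.** With the same assumed SDs, the sum of squares is 1414 + 454 = 1868, so the pooled SD is √(1868/8) = 15.3. The correct SD at each time is √((s1² + s2²)/2):

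- 30 min: 21.5; ratio 0.71; rejection about 16 to 18%.
- 2 h: 10.7; ratio 1.43; under 1%.
- 4 h: 6.7; ratio 2.29; about 0%.
- 24 h: 17.7; ratio 0.86; about 9%.

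Welch at each time gives about 5%. Using the pilot values alone, read as SDs, the pooled SD is √((0.01² + 0.25² + 2.4² + 1.2²)/4) = 1.347. With 50 per arm its SE is 0.269, against 0.0354 at 2 h (7.6 times too large, rejection about 0%) and 0.379 at 6 h (ratio 0.71, rejection 16.4%).

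**The case against.** The strongest reply is that the plan does not commit the larger error. A reader might infer that the planned methods pool variance over both arms and times, so that the %IPA error bars at single time-points are wrong. The documents do not support this. Student t at one time-point uses that time's data only, and with equal arms its SE is exactly the unequal-variance SE. The results in step 4 need an error term that the plan never names, and the t test appears in the very next sentence. If it serves the 2 h comparison, step 4 does not apply. The planned display is mean ± SD, which involves no pooling, and the plan mentions no confidence intervals. All this stands.

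Nor does the pilot show that the assumptions fail here. It enrolled NSTEMI patients, gave ticagrelor plus eptifibatide in both arms, and reports a 6 h sample that this trial does not take. Its 2 h values are also doubtful as SDs. With 35 per arm (assumed), a 1-point difference would give t = 1/√((0.01² + 0.25²)/35) ≈ 24, yet the text reports no significant difference. Read as SEs, t is about 4, or about 2 if rounding hides a difference of only 0.5. One sentence in Statistical Analysis also places eptifibatide in both arms, contrary to Methods and End-Points. The passages must be reconciled, and the design argument rests on the latter two.

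Finally, the trial calls itself exploratory, and no passage suggests a 20% loss of samples in one arm. These points limit the size of the concern. They do not answer the silence on unequal variance, on sphericity, or on which test is primary.

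**Conclusion.** The point holds as a free improvement. Equal variance and sphericity are doubtful for %IPA, on indirect pilot evidence and on the sponsor's own account of the drugs, and the plan protects against neither failure.

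- Student t: near nominal with equal arms; roughly 3% to 8% at 40 vs 50 evaluable patients under the assumed SD of 15 vs 1.
- Uncorrected arm-by-time F: about 7% under the assumed four-time SDs.
- Time-pooled contrasts: far too conservative at 2 h and anti-conservative where spread is large, but only if that error term were used.

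The exact sizes rest on assumed SDs and normal data, and normality is itself questionable near the ceiling.

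**What to change.** In Statistical Analysis, replace the two %IPA methods with wording to this effect: the primary 2 h comparison, and the comparison at each other time-point, will use the Welch (unequal-variance) t test with a 95% CI for the difference in means. No comparison at a single time-point will use an ANOVA error pooled over times. Any overall arm-by-time effect will be tested with the Greenhouse-Geisser correction or the multivariate test.

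The cost is a few lines of text. SPSS already prints the unequal-variance line and the corrected and multivariate tests. Welch loses essentially nothing if the variances prove equal. No change to sample size, sampling times or data collection is needed.

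### Must the plan say which ADP concentration, 5 or 20 micromolar, decides the primary endpoint at 2 h?

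*Combined protocol and SAP*

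**What the plan says.** The Light-Transmittance Aggregometry section commits to two ADP concentrations: "Platelet aggregation induced by ADP (5 and 20" micromolar), with TRAP also at two concentrations. It then lists two read-outs: "The final extent of aggregation, measured at 6 minutes after agonist addition, and the maximal extent of aggregation will be expressed" as a percent change in light transmittance. The IPA formula that follows is defined without choosing between them: "Where PA is platelet aggregation, b is predosing, and t is postdosing".

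End-Points names one primary comparison, in the singular, at one time: "The primary end point of the study is to compare %IPA induced by ADP at 2 h". The secondary endpoints use the same general term: "Secondary endpoints of the study are to compare %IPA induced by ADP and TRAP", at all time-points.

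Statistical Analysis labels the trial exploratory and says that no power calculation was done. It states that P < 0.05 "will be considered statistically significant", and gives neither a multiplicity rule nor a concentration. Anticipated Findings and the platelet-testing row of Table 1 name no concentration either. Fig. 2 (study design) is not reproduced in the text available, so this reading covers the visible text only.

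The background describes the sponsor's earlier 70-patient study and gives results for both concentrations: "there were no significant difference in the %IPA values at 2 h and 6 h with ADP 5" micromolar, "and with ADP 20" micromolar as well.

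**The concern.** A primary endpoint should identify one variable before the data are seen. Here two measured variables fit the description, or four if the final and maximal read-outs are counted separately. If ADP 5 and ADP 20 gave opposite verdicts at 2 h, the plan would not say which is the trial's answer, and the choice could be made after seeing the results.

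That could work in either direction. A significant concentration could be put forward as evidence of a difference. A non-significant one could be quoted in support of the similarity at 2 h that Anticipated Findings expects. The Rationale says that a favourable result would lead to a large randomized trial, so the label on the primary result has some weight.

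**Working it through.** **The text.** There is no stated power or derived sample size to reproduce, so the first check is whether any section closes the gap.

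| Section | What it says about ADP concentration |
|---|---|
| Background (70-patient study) | 5 and 20 micromolar both reported, neither ranked |
| Light-Transmittance Aggregometry | 5 and 20 micromolar both measured, neither ranked |
| Statistical Analysis | none named |
| End-Points, primary | ADP, no concentration |
| End-Points, secondary | ADP and TRAP, no concentration |
| Anticipated Findings | none named |
| Table 1 | platelet function testing, no agonist |

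None does. Equally, no section says that both concentrations are primary, or that either is enough. The wording leaves the variable open; it does not prescribe two tests.

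**What the opening could be worth.** The inputs are two-sided α = 0.05 (the threshold is in Statistical Analysis; two-sidedness is assumed), two variables, and equal standardised effects (assumed). The correlation ρ between the two test statistics is not in the documents, so a range of 0.5 to 0.95 is used. The model is bivariate normal, with each test significant when |z| > 1.96.

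*No true difference.* P(either significant) = 1 − P(|Z₁| ≤ 1.96 and |Z₂| ≤ 1.96). Since P(both) = 2α − P(either), P(opposite verdicts) = 2 × P(either) − 2α.

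| ρ | Either significant | Opposite verdicts |
|---|---|---|
| 0.95 | 6.46% | 2 × 6.46 − 10 = 2.9% |
| 0.9 | 7.04% | 2 × 7.04 − 10 = 4.1% |
| 0.8 | 7.81% | 2 × 7.81 − 10 = 5.6% |
| 0.5 | 9.07% | 2 × 9.07 − 10 = 8.1% |

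Independence would give 1 − 0.95² = 9.75%, the ceiling over non-negative correlations.

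*A true difference, at an assumed power for each test.*

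| ρ | Opposite verdicts, 80% power | Opposite verdicts, 50% power |
|---|---|---|
| 0.95 | 7.1% | 10.1% |
| 0.9 | 10.0% | 14.4% |
| 0.8 | 14.2% | 20.5% |
| 0.5 | 22.6% | 33.3% |

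At 80% power, the chance that at least one concentration is non-significant is 20% plus half the disagreement rate: 20 + 10.0/2 = 25.0% at ρ = 0.9 and 20 + 14.2/2 = 27.1% at ρ = 0.8, against 20% for a single named concentration.

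**What these figures cover.** They describe a test of difference. The Rationale hypothesises non-inferiority and no margin is given, so no corresponding error rate can be computed for that aim.

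**The case for a change.** The strongest case for a change is that it would be almost free: a sentence in End-Points and a clause defining PA, with no extra samples or patients. Calling a trial exploratory does not remove the need to know what its named primary endpoint is. Reporting both concentrations shows a disagreement but does not say which one decides. Even at a correlation of 0.95, opposite verdicts would occur in 7.1% of trials at 80% power, and more often at lower correlations.

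Much of this stands. The definition is incomplete, and a split result would have no pre-set reading. Three things limit it.

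- The false-positive figures need a rule that either concentration suffices, and the plan contains no such rule. They also concern a claim of difference, which is not the stated hypothesis.
- Quoting a non-significant result as similarity is a weak inference even with one named concentration. Naming one would not repair it, and the 5 to 7 point change (25.0% or 27.1% against 20%) rests on a power that the plan never claims.
- There is no single right way to close the gap. Naming one concentration, requiring both to agree, averaging them, or adjusting for two would each be legitimate. The documents give no reason to call any present choice wrong.

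**Conclusion.** The concern describes an unwritten definition, not an error, and does not call for a change to the plan. End-Points leaves the ADP concentration open, and the aggregometry section leaves the read-out open. No stated rule, formula or number becomes wrong as a result. Both concentrations are to be measured, so an analyst can present the 2 h comparison for each, side by side, with the read-out stated. The earlier study reported both concentrations, with no sign of selection. A reader would then see whether the two agree, which is what an exploratory, unpowered pharmacodynamic comparison can fairly offer.

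The possible effect is modest for false positives: 6.5% to 9.1% against 5% if either concentration could carry a claim of difference, at assumed correlations of 0.95 to 0.5. Disagreement between the two could be more frequent, 7.1% to 22.6% at an assumed 80% power over the same correlations, but it would be visible in the report. These figures are illustrations that rest on assumed correlations, power and equal effects. For non-inferiority nothing can be quantified, because no margin is stated. The judgement depends on both concentrations being reported and on the result being read as exploratory; a confirmatory claim resting on one concentration alone would need the variable fixed beforehand.
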